The OLE Phase is an optional 48 week open-label treatment phase following the double-blind phase of the study. All subjects who enter the OLE phase will sign a new informed consent form.

All participants must have their Week 48 visit in-person prior to enrolling in the OLE phase. Due to COVID-19, the timing of this visit may be delayed.

Participants who early-terminated from the double-blind phase of the trial or who discontinued the study medication for any reason will not be eligible for enrollment in the OLE phase.

When a site is open for recruitment to the OLE Phase, participants completing the double-blind treatment phase who choose to participate in the OLE phase and are eligible to continue, must consent to the OLE phase and directly enter the OLE phase starting at Week 48 visit of the double-blind treatment phase. The Week 48 visit will serve as the Baseline-Extension visit in the OLE phase for participants who move directly from the double-blind treatment phase to the

OLE. Thereafter, participants will undergo visits at Week 2-Extension, Week 4-Extension, Week 8-Extension, Week 12-Extension, and then every 12 weeks of the OLE phase as outlined in Appendix II: Schedule of Assessments and Events – Open-Label Extension Phase.

A participant who has completed the double-blind treatment phase of the study prior to the OLE phase of the study being approved and open for recruitment at the study center where they are participating, can reconsent and start the OLE phase as long as the investigator determines that open-label treatment offers an acceptable risk-benefit profile for the participant. Once the study site is open for recruitment for the OLE, study participants who previously completed the double-blind phase of the study will have up to approximately 12 weeks (from the date of OLE opening at the site) to enroll and complete the OLE Baseline-Extension Visit, regardless of their date of double-blind phase completion.

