4 ANALYSIS SETS, TREATMENT GROUPS, AND SUBGROUPS

4.1 Analysis Sets

The following populations will be evaluated and used for presentation and analysis of the data:

- Enrolled subjects: Subjects who signed an informed consent form and were assigned a Patient Identification number (PID).
- Randomized subjects: Enrolled subjects who received a treatment assignment from the IWRS.
- Treated/Safety: Enrolled subjects who received at least 1 dose of blinded study therapy (Verdiperstat or placebo).
- Modified Intent-to-Treat (mITT) subjects: Randomized subjects who received at least one dose of blinded study therapy and provided a baseline and at least one post-baseline efficacy assessment.
- Open-Label Extension Treated subjects: Enrolled subjects in the extension phase who received at least 1 dose of open-label study therapy (Verdiperstat).
- Verdiperstat Treated Participants: Enrolled subjects who received at least 1 dose of Verdiperstat (blinded or open-label)

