6.1.1.1 Tables

Unless otherwise specified, the DB Phase and OLE Phase will be analyzed separately. For tables summarizing subjects who received at least one dose of DB or OLE study medication (Verdiperstat), summary statistics will be calculated from both phases combined for subjects randomized to Verdiperstat and from the OL Extension Phase for subjects randomized to placebo.

Treatment Group Presentation

Tables present results by treatment group (i.e., Verdiperstat and placebo) with the following exceptions:

- Results for the enrolled analysis set are presented only by overall, without treatment group.
- Results for study population parameters (see Section 6.2) and pre-treatment safety also include overall.

• OLE tabulations will include the sequence of the treatment, i.e., Verdiperstat/ Verdiperstat or Placebo/ Verdiperstat.

Time-to-event Tables

Time-to-event endpoints are summarized with KM tables displaying the following at each time interval:

- Number of subjects at risk, defined as those who did not have the event just prior to the start of the interval and who were not censored prior to the interval
- Number of subjects with events, defined as those who had the event for the first time during the interval
- Number of subjects censored, defined as those who did not have the event and whose censoring date/time (e.g., last contact date, last available measurement date/time) is in the interval
- Cumulative probability of having the event with lower and upper 95% CI limits, based on the KM product limit method.

Time-to-event distributions of endpoints are tabulated with the following descriptive statistics: number and percentage of subjects with events; number and percentage of subjects censored in or before the last time interval; number and percentage of subjects censored in the last time interval; time-to-event median, first quartile, and third quartile, with 95% CI. The 95% CI for the median is estimated using the method of Brookmeyer and Crowley.

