The number and percentage of subjects who had dose titrations during the OLE phase will also be summarized by time point and dose.

Double-Blind and Open-Label Extension Phases Combined

For the combined phase data, the extent of subject exposure (i.e., treatment duration) to Verdiperstat during the entire study will be quantified as the number of days on study medication (Verdiperstat) and measured from the time the subject received the first dose of Verdiperstat until the time the subject received the last dose of Verdiperstat, either at the end of the study or withdrawal from the double-blind or OLE phases. Treatment Duration includes missed dose days within a study phase and excludes the dosing break between study phases (i.e., (last dose day of Verdiperstat study medication – first dose date of Verdiperstat study medication + 1) – (number of days with a dosing break between the double-blind and OLE phases)).

The extent of subject exposure (i.e., total days on Verdiperstat) during the entire study will also be calculated to exclude days when subjects missed a dose (i.e., Treatment Duration – number of days a subject missed all doses of study medication).

Additionally, percent (%) compliance will be calculated as (total days on Verdiperstat study medication) / (Treatment Duration of Verdiperstat study medication) × 100.

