6.4 Safety

Safety and other analyses will be conducted on treated subjects by treatment group. For the DB Phase outputs, treated subjects in the DB Phase will be used; for the OLE Phase outputs, treated subjects in the OLE Phase will be used; and for the combined phase outputs, DB and OLE Verdiperstat treated subjects will be used. All safety and other data will be listed for the entire study with screening, DB Phase, and OLE Phase data presented together.

Safety outcome measures include extent of exposure, compliance to study treatment, AEs, laboratory assessments, vital signs, ECGs, concomitant medications, and the S-STS questionnaire.

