7 CONVENTIONS

7.1 Analysis Periods

Analysis periods are defined as follows:

- Screening phase: to include all assessments on or before the first day of study drug.
- Pre-treatment: measurement date/time on or before the study drug first dose date/time. This period is used to derive baseline values.
- On-treatment in the double-blind phase: to include all assessments after the study drug first dose date/time in the double-blind phase and up to the first day of OLE phase study drug or (last day of DB phase study drug + 7 days for efficacy or 30 days for safety), whichever is earliest, for subjects entering OLE or through the double-blind phase study drug last dose date/time + 7 days to assess efficacy endpoints and + 30 days to assess safety endpoints on treatment.
- On-treatment in the OLE phase: to include all assessments after the open label study drug first dose date/time through the study drug last dose date/time + 7 days to assess efficacy endpoints and + 30 days to assess safety endpoints on treatment
- On-treatment in the study: to include any Verdiperstat treatment (double-blind or OLE phase), and all assessments after the first dose date/time up to the last dose date/time + 7 days to assess efficacy endpoints and + 30 days to assess safety endpoints on treatment, excluding the number of days with a dosing break between the double-blind and OLE phases (applicable if dosing break >30 days).

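### The combined-phase exposure formula also subtracts the between-phase dosing break from subjects who took placebo first, understating their verdiperstat duration by exactly the length of the break

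*SAP*

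**What the plan says.** The combined-phase part of SAP 6.2.6.1 sets the interval for verdiperstat exposure as "measured from the time the subject received the first dose of Verdiperstat until the time the subject received the last dose of Verdiperstat". It keeps missed-dose days within a phase, excludes the break between phases, and gives the formula that ends "first dose date of Verdiperstat study medication + 1) – (number of days with a dosing break between the double-blind and OLE phases". Total days on verdiperstat is that duration minus days on which all doses were missed. Percent compliance is total days divided by that duration.

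Subjects who took placebo first are in these outputs. SAP 4.1 defines the verdiperstat-treated set as "Enrolled subjects who received at least 1 dose of Verdiperstat (blinded or open-label", closing the bracket there, and SAP 6.4 says that "for the combined phase outputs, DB and OLE Verdiperstat treated subjects will be used". SAP 6.1.1.1 names Placebo/Verdiperstat as one of the two OLE sequences. For tables of subjects who received verdiperstat in either phase, it takes statistics "from both phases combined for subjects randomized to Verdiperstat and from the OL Extension Phase for subjects randomized to placebo".

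The OLE-only part of SAP 6.2.6.1 defines duration as last minus first OLE dose date plus one, with no break term.

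SAP 2.1 foresees breaks. It has a separate route for participants off study drug for more than 4 weeks. Subjects who finished the double-blind phase before their site opened the OLE have about 12 weeks from that opening to enter, "regardless of their date of double-blind phase completion".

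**The concern.** The formula suits only one of the two OLE sequences. A subject who took placebo first has no verdiperstat before the OLE, so the first-to-last span for verdiperstat is simply the OLE span. Subtracting the between-phase break takes off days that were never counted.

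The SAP would then report two different durations for the same doses in the same subject: one in the OLE exposure table and a shorter one in the combined table. SAP 6.4 lists extent of exposure and compliance among the safety outcome measures, and the combined table is where cumulative exposure to verdiperstat is summarised. Durations that are too short, and occasionally zero or negative, would pull down its means and minima.

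**Working it through.** The SAP states no numerical exposure result, so there is no figure to reproduce. The check applies its formulas to each sequence.

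**Inputs.** The formulas and sequences are those of SAP 6.2.6.1 and 6.1.1.1. Let P be days of double-blind dosing, B the break in days, D the days from first to last OLE dose inclusive, and m the OLE days on which all doses were missed. The planned OLE is 48 weeks (SAP 2.1): 48 × 7 = 336 days. The values of B, the shorter values of D and the 5% missed-day rate below are assumptions, because the documents give none.

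**Verdiperstat/Verdiperstat.** The span is P + B + D. The formula gives (P + B + D) − B = P + D, which is correct. Example: P = 336, B = 84, D = 336 gives 756 − 84 = 672 = 336 + 336.

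**Placebo/Verdiperstat.** The first verdiperstat dose is OLE Day 1, so the span is D. The combined formula gives D − B and the OLE formula gives D. The shortfall is B.

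| B (assumed) | D | Combined formula, D − B | OLE formula, D | Shortfall |
|---|---|---|---|---|
| 0 | 336 | 336 | 336 | 0 |
| 28 | 336 | 308 | 336 | 28 (8%) |
| 84 | 336 | 252 | 336 | 84 (25%) |
| 168 | 336 | 168 | 336 | 168 (50%) |
| 84 | 84 (assumed) | 0 | 84 | 84 |
| 84 | 14 (assumed) | −70 | 14 | 84 |

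The result is zero when B = D and negative only when B > D.

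**Total days on verdiperstat.** The formula gives D − B − m instead of D − m, so the shortfall is again B.

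**Compliance.** The formula gives (D − B − m)/(D − B) instead of (D − m)/D. The two agree when m = 0 and B ≠ D. With D = 336 and 5% of days missed (m = 17):

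- Correct: 319/336 = 94.9%.
- B = 28: 291/308 = 94.5%.
- B = 84: 235/252 = 93.3%.
- B = 168: 151/168 = 89.9%.

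At B = D the ratio is undefined. At B > D with m > 0 it exceeds 100%: B = 84, D = 14, m = 1 gives (−71)/(−70) = 101.4%, against 13/14 = 92.9%.

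**After correction.** Subtracting the break only when it lies between the first and last verdiperstat dose gives D for Placebo/Verdiperstat at any B, equal to the OLE formula. Verdiperstat/Verdiperstat stays at P + D.

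**The case against.** The best defence is that the intent is clear. The same paragraph confines the measure to verdiperstat, from first to last dose, and describes the break as something to exclude. For a subject who took placebo first there is nothing inside the interval to exclude. SAP 6.1.1.1 adds that statistics come "from the OL Extension Phase for subjects randomized to placebo" in tables of this kind. A programmer who follows that rule could reach the right number, and the correct duration for these subjects is planned anyway in the OLE tabulations.

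This shows what was meant, but it does not repair the formula. The rule in 6.1.1.1 says which phase supplies the data; it does not cancel the explicit subtraction. A programmer who uses OLE dates and then codes the formula as written still gets D − B. Nor can the break be read as zero for these subjects. It is defined between study phases, and SAP 2.1 counts time off study drug for OLE entrants without regard to arm.

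The defence does limit the size. SAP 2.1 has completers at a site already open to the OLE enter directly at Week 48, so those with no break show no error. Negative durations are an edge case that output checks would probably catch.

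A reader might infer that SAP 7.1 carries the same error, because its study-wide on-treatment period is defined as "excluding the number of days with a dosing break between the double-blind and OLE phases (applicable if dosing break >30 days", closing the bracket there. The documents do not support this. That text defines which assessments count as on treatment and computes no duration. For a subject who took placebo first the window opens after the break, so excluding the break removes no assessment.

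**Conclusion.** The combined-phase formula in SAP 6.2.6.1 is wrong as written for subjects who received placebo in the double-blind phase and had a break before the OLE. It conflicts with its own first-to-last-verdiperstat definition, with the OLE formula in the same section, and with the table rule in SAP 6.1.1.1. The understatement per subject equals the break exactly. That result needs no assumption beyond applying the formula literally; the 8%, 25% and 50% figures rest on assumed breaks and a full 336-day OLE.

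The effect on total exposure cannot be sized, because neither the number of affected subjects nor their break lengths is given. It would equal the sum of the breaks over those subjects. SAP 2.1 sets no upper limit on a break measured from double-blind completion, so long ones cannot be ruled out.

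It would be too strong to infer that the trial's efficacy conclusions or safety event counts are affected. The formula feeds only the descriptive combined-phase exposure and compliance summary. It should be corrected before programming, but it has no bearing on the primary analysis.

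**What to change.** In the combined-phase part of SAP 6.2.6.1, define duration as the sum of the phase durations in which verdiperstat was actually received: double-blind last minus first dose date plus one, if verdiperstat was received in that phase, plus OLE last minus first dose date plus one, if the OLE was entered. Equivalently, keep the present formula and subtract the break only for subjects who received verdiperstat in both phases.

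The condition should follow treatment received rather than treatment assigned, because SAP 4.2 and 6.2.6 present exposure by as-treated group. Total days and compliance then correct themselves, and the combined and OLE tables agree for the Placebo/Verdiperstat sequence. No change to SAP 7.1 is needed.

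The cost is one sentence in the SAP and one programming condition. No new data are required, and results for subjects who took verdiperstat in both phases do not change.

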6.2.6.2 Prior and Concomitant Non-study Medications

Prior and concomitant medications will be coded using the WHO Drug Global B3 March 2021. Results will be tabulated by Anatomic Therapeutic Class (ATC) and PT by treatment group and overall.

Prior medications are defined as those start or stop date < IWRS enrollment date – 14 days. Unless the start date of the medication is after the last DB study drug dose date, or the end date of the medication is prior to the start date of the study drug, the medication will be considered 'concomitant.' For medication with partial start/stop date, if it cannot be definitively shown that the medication was not taken during the DB treatment period, the medication is included as concomitant.

All prior, concomitant, and follow-up medications will be listed.

[figure not shown]

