- k. Must have reliable caregiver to accompany subject to study visits, with the same caregiver completing caregiver assessments at Baseline, Week 24 and Week 48/Early Discontinuation, when possible. Caregiver must be able to read, understand, and speak local language fluently to ensure comprehension of informed consent and protocol-specified assessments. Caregiver must also have frequent contact with subject (at least 3 hours per week at one time or different times) and be willing to monitor the subject's health and concomitant medications throughout the study.
- l. If subject is receiving treatment for MSA, the doses must have been stable for at least 30 days prior to Baseline/Randomization and medications present at Baseline expected to remain relatively stable during the study period. This may include medications commonly used for Parkinson's disease (e.g., coenzyme Q10, levodopa/carbidopa, levodopa/benserazide, fava bean extract, a dopamine agonist, catechol-O-methyltransferase inhibitor, amantadine) or those for autonomic dysfunction (e.g., ephedrine, midodrine, fludrocortisone, octreotide, desmopressin, oxybutynine, droxidopa).

- m. Stable on other chronic medications and supplements for at least 30 days prior to Baseline/Randomization and expected to remain relatively stable during the study period.
- n. Women of child bearing potential (WOCBP) [see protocol section 5.5] and fertile men (including those vasectomized for less than 6 months) with female partners who are WOCBP (not surgically sterile and not postmenopausal) [see protocol section 5.5] must agree to use highly effective birth control, including two methods of contraception, for the duration of the study (i.e., beginning 30 days prior to Baseline/Randomization and extending to 30 days for women and 90 days for men after the last dose of study drug). The two methods of contraception should include:
 - i. one barrier method (e.g. diaphragm with spermicide, condom with spermicidal gel, cervical cap);
 - ii. and one other method that could include hormonal contraceptives (e.g. oral contraceptives, injectable contraceptives, contraceptive implant, patch) used for at least 4 weeks prior to sexual intercourse (Section 5.5);
- o. WOCBP must have a negative serum pregnancy test at Screening and a negative urine pregnancy test within approximately 24 hours prior to dosing at Baseline/Randomization.

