7.2 Dose and Administration

7.2.1 Method of Assigning Patient Identification

The Investigator or designee will need to access an Interactive Web-based Response System (IWRS) in order to register each subject. Initially, after informed consent is obtained at the Screening Visit, the Investigator or designee will enter the subject into the study and obtain a subject number assignment. After completion of Screening evaluations, all eligible subjects will be randomized, in a 1:1 ratio to receive either BHV-3241 (600 mg BID) or matching placebo. Randomization will be stratified by disease subtype of either MSA-P vs. MSA-C, diagnostic category of possible MSA vs. probable MSA, and country. Container assignments will be obtained by the Investigator (or designee) via the IWRS system.

Investigational sites will access the IWRS at each scheduled visit throughout the double-blind phase of the study (except for Weeks 2, 8 and 48) to track patient enrollment and dispense drug. Study medication will be assigned via the IWRS system; the system will assign specific container numbers for all blinded study drug to be dispensed to the subject. Once a container has been assigned it cannot be dispensed to another study subject.

After a subject has provided informed consent to participate in the OLE phase, the Investigator or designee will access the IWRS to register the subject's OLE participation and at each scheduled visit throughout the OLE phase of the study (except for Weeks 2-Ext, 4-Ext, 8-Ext and 48-Ext) to track patient enrollment and obtain container numbers of open-label BHV-3241 to be dispensed to the subject. Once a container has been assigned it cannot be dispensed to another study subject.

Sites will be responsible for recording the container numbers dispensed to the subject on the Drug Accountability Form provided in the Regulatory Binder, as well as ensure appropriate documentation of dispensation in the subject's medical record.

Once a subject completes the study, or if a subject is discontinued early from the study, the Investigator or designee must access the IWRS to document discontinuation of the patient from participation in the study.

Rescreening: If initial Screening lab sample results do not meet protocol-specified eligibility criteria and the Investigator determines that a repeat sample may meet the range required for eligibility, a repeat lab sample may be collected (one repeat collection/analysis allowed).

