2 STUDY DESCRIPTION

2.1 Study Design

Verdiperstat is a Phase 3, multicenter, randomized, double-blind, 2-arm placebo-controlled parallel-group study designed to evaluate the efficacy and safety of Verdiperstat in a population of patients with MSA (MSA-C and MSA-P). The study is planned to consist of a Screening phase lasting a maximum of approximately 6 weeks and a randomized double-blind treatment phase of approximately 48 weeks, per Figure 1. It is anticipated that the Randomization phase will include a dose titration period of approximately 2 weeks followed by a full dose period of approximately 46 weeks. Approximately 325 subjects in total are planned to be randomized in a 1:1 ratio to receive either Verdiperstat 600 mg BID, or matching placebo BID. It is anticipated that subjects will be assessed at clinic visits, per the Schedule of Assessments & Events (Appendix I: Schedule of Assessments and Events – Randomized Double-blind Phase). In addition, subjects who are completing or have completed Week 48 of the double-blind treatment phase may be offered the opportunity to enroll in an OLE phase, in which subjects will receive open-label treatment with Verdiperstat for approximately 48 weeks (Appendix II: Schedule of Assessments and Events – Open-Label Extension Phase).

Figure 1: Study Schematic

Screening Phase

The purpose of the Screening phase is to ensure that the appropriate subjects are entered into the trial and remain stable during the pre-treatment period. It is estimated that approximately 360 subjects will enter the Screening phase of the trial. The Investigator will determine that the subject meets eligibility criteria and will collect demographic and medical data presenting a full characterization of the subject. All attempts should be made to obtain medical and pharmacy records to confirm the subject's medical and medication treatment history. During Screening,

Biohaven (or designee) may review relevant clinical information to confirm the diagnosis and subtype of MSA, for study eligibility and stratification prior to randomization. Screening will range from a minimum of 1 day to a maximum of 42 days.

If initial Screening lab sample results do not meet protocol-specified eligibility criteria and the Investigator determines that a repeat sample may meet the range required for eligibility, a repeat lab sample may be collected (one repeat collection/analysis allowed).

Rescreening

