6.2.5 Baseline Characteristics

Baseline characteristics include (1) demographics and other relevant baseline characteristics, (2) medical and psychiatric history, (3) prior non-study medications, and (4) prior Parkinson's medications.

Baseline characteristics are tabulated for treated subjects, for subjects enrolled but not treated, and for Verdiperstat treated subjects.

Demographic and other baseline data will also be provided in by-subject listings.

Baseline is defined according to analysis set as follows:

- Enrolled but not treated: Last non-missing value
- Treated subjects: Last non-missing value at or before the study drug start date/time.

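### The SAP's date rules for prior and concomitant medicines leave an uncovered span of up to 56 days before first dose, so the baseline medication tables can omit therapy in use at entry

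*SAP*

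**What the plan says.** SAP 6.2.6.2 sets two date rules. For the prior class: "Prior medications are defined as those start or stop date < IWRS enrollment date – 14 days". A medicine is concomitant unless it started after the last double-blind dose, "or the end date of the medication is prior to the start date of the study drug". A fallback covers partial dates: "if it cannot be definitively shown that the medication was not taken during the DB treatment period, the medication is included as concomitant". The section ends by promising a listing of prior, concomitant and follow-up medicines.

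SAP 6.2.5 names four components of the baseline characteristics. The last two are "3) prior non-study medications, and (4) prior Parkinson's medications". It gives no separate definition of *prior*.

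The term *IWRS enrollment date* is not defined. Protocol 7.2.1 says that "after informed consent is obtained at the Screening Visit, the Investigator or designee will enter the subject into the study". SAP 4.1 defines enrolled subjects by consent and an assigned patient number, and randomized subjects as a separate set. Where the SAP means randomization (6.2.2 and 7.2), it says IWRS randomization date. On length, SAP 2.1 says "Screening will range from a minimum of 1 day to a maximum of 42 days".

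For MSA treatment, inclusion criterion 3l (Protocol 5.2) requires that "the doses must have been stable for at least 30 days prior to Baseline/Randomization".

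**The concern.** A prior/concomitant classification should place every recorded pre-dose medicine in at least one class. Here the prior rule looks back from a date that can be weeks before dosing, and then a further 14 days, while the concomitant rule begins at first dose. Nothing covers the time between.

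Two consequences follow from the text. A short course taken wholly inside the span has no class, and so no table. A medicine started inside the span and continued into treatment has a class, but not the one that the baseline tables use.

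At stake is the description of the arms at entry. A reader would expect the prior-medication tables to show the background symptomatic treatment that subjects were on when baseline UMSARS was rated. Therapy started shortly before or during screening would be left out of them.

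**Working it through.** The plan states no figure on this point, so there is none to reproduce. The check applies the two date rules as written.

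**Inputs.** First dose is on Day 1, and there is no Day 0 (schedule of assessments; SAP 2.1). Screening lasts 1 to 42 days (SAP 2.1). The look-back is 14 days (SAP 6.2.6.2). The stability requirement is 30 days (Protocol 5.2, criterion 3l).

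**Formulas.** Let IWRS enrollment fall on Day −s.

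- Cutoff = Day −(s + 14). The inequality is strict, so a date on the cutoff itself is not prior.
- Uncovered span = Day −(s + 14) to Day −1, which is s + 14 days.
- Start days that lie in the span and still satisfy 30 days of stability run from Day −(s + 14) to Day −30. Their number is (s + 14) − 30 + 1 = s − 15, if positive.

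| Enrollment date taken as | Cutoff | Uncovered span (days) | Eligible start days not counted as prior |
|---|---|---|---|
| Day −42 | Day −56 | 56 | 27 (Day −56 to −30) |
| Day −28 | Day −42 | 42 | 13 (Day −42 to −30) |
| Day −16 | Day −30 | 30 | 1 (Day −30) |
| Day −15 | Day −29 | 29 | 0 |
| Day −1 | Day −15 | 15 | 0 |
| Randomization, Day 1 | Day −14 | 14 | 0 |

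**Worked cases, enrollment on Day −42 (cutoff Day −56).**

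- Midodrine taken from Day −50 to Day −31: neither date is before Day −56, so it is not prior. It ended before Day 1, so it is not concomitant. It is in neither table. The partial-date fallback does not help, because both dates are complete.
- Levodopa started on Day −45 and ongoing: its start is not before Day −56, so it is not prior. It is ongoing at Day 1, so it is concomitant. It has been stable for more than 30 days, so the subject is eligible, yet it is absent from the baseline table of prior Parkinson's medicines.
- A drug started on Day −90 and stopped on Day −20: its start is before Day −56, so it is prior. It is counted.

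**Data available.** Protocol 5.4 has sites record medicines taken from one month before enrollment. This reaches back beyond the 14-day cutoff, so medicines in the span are collected. Only the flag misses them.

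**The case against.** The strongest reply is that little is lost and nothing inferential depends on it. Most of that stands.

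- A reader might infer that any symptomatic drug stopped during screening disappears from the summary. It does not. The rule accepts a start *or* a stop date, so an established drug withdrawn in screening stays prior through its start date. Criterion 3l also makes a stop of MSA treatment in the last 30 days unlikely. The unclassified group is therefore confined to courses both begun and ended inside the span.
- A reader might infer that ongoing Parkinson's therapy started in the span is lost altogether. It is not. It appears in the concomitant table by treatment group, and it should count in the SAP 4.3 subgroup, which is based on concomitant use. The loss is from the baseline tables only.
- A reader might extend the Parkinson's-table point to drugs for autonomic dysfunction. Criterion 3l names these separately from Parkinson's medicines, and nothing shows that they belong in that table. For them, the point concerns the general prior-medication table.
- SAP 6.2.5 does not say in terms that the 14-day rule governs its tables, and table specifications are in a separate document (SAP 6.1.1). This is fair. However, 6.2.6.2 gives the only definition of *prior* in either document.
- *IWRS enrollment date* could mean randomization. The wording elsewhere points to screening registration. On the other reading a 14-day span remains, but no Parkinson's therapy meeting the 30-day criterion is dropped.
- SAP 6.4 promises listings of all safety and other data, screening included, and counts concomitant medications among the safety measures. Medicines in the span may therefore still be visible by subject. A listing does not repair a summary table.

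**Conclusion.** The rules as written do not cover every recorded pre-dose medicine, and if followed they give incomplete baseline medication tables. The uncovered span is 15 to 56 days if IWRS enrollment is the screening registration, and 14 days if it is randomization. The 56 days is a maximum: it needs the full 42-day screening and assumes a single screening. The documents do not say which enrollment date applies after rescreening.

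For Parkinson's therapy meeting the 30-day criterion, omission from the baseline table requires the screening reading, enrollment at least 16 days before first dose, and a start on one of at most 27 days.

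The effect is descriptive only. Prior or concomitant status enters no efficacy model (SAP 6.3.1, 6.3.2.1), and subgroup results are descriptive (SAP 6.3.2.4). A reader might want a count of affected subjects, but the documents give no rate of new starts in this period. Any percentage applied to the 325 planned subjects would be a guess. This is a minor point, worth correcting because the correction is simple.

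**What to change.** Replace the first sentence of the definition in SAP 6.2.6.2 with: *Prior medications are those with a start date or a stop date before the date of first double-blind dose; those ongoing on that date are also concomitant.* State in SAP 6.2.5 that this flag defines both the prior non-study and the prior Parkinson's medication tables.

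Keeping the stop-date limb matters: it classifies a medicine whose start date is unknown but which is known to have ended before dosing. The partial-date fallback stays as it is, and medicines started after the last double-blind dose remain follow-up medications. The uncovered span becomes 0 days, and the undefined enrollment date is no longer needed in this rule. Because 6.2.5 also tabulates subjects who were enrolled but never treated, and who have no first dose, add a clause saying how their recorded medicines are classed.

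The cost is a sentence or two in the SAP and one reprogrammed date flag before database lock. No new data are needed.
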